10.4.5 ADHERENCE AND RETENTION ANALYSES

Adherence to the randomized intervention will be assessed by telephone interview and in person interview during follow up.

10.4.6 BASELINE DESCRIPTIVE STATISTICS

We plan to compare the baseline descriptive statistics between the treatment and control groups and establish if there is a significant difference of any variables. For continuous variables, a two sample t-test will be used to compare data that appear to be normally distributed (Wilcoxon Rank Sum test for skewed data). For categorical data, Pearson's Chi-square test of independence will be used.

10.4.7 PLANNED INTERIM ANALYSES

None

10.4.7.1 SAFETY REVIEW

NO statistical plan for safety review.

10.4.7.2 EFFICACY REVIEW

Not applicable

10.4.8 ADDITIONAL SUB-GROUP ANALYSES

No additional sub-group analyses are needed for this pilot study.

10.4.9 MULTIPLE COMPARISON/MULTIPLICITY

NA

10.4.10 TABULATION OF INDIVIDUAL RESPONSE DATA

NA

Version 01.2 Protocol:201607761 06/28/2017

10.4.11 EXPLORATORY ANALYSES

Change in VRTCO₂

Mean change VRTCO₂ between drug and placebo will be compared. The mean and standard deviation estimates of the differences will be provided.

Change in time to VRTCO₂

Mean change in time to VRTCO₂ between drug and placebo will be compared. The mean and standard deviation estimates of the differences will be provided.

Change in time to end of HCVR testing

Mean change in time to end of HCVR testing will be compared between drug and placebo. The mean and standard deviation estimates of the differences will be provided.

10.5 SAMPLE SIZE

No formal sample size calculation is performed because the primary puporse of the project is assess feasibility.

10.6 MEASURES TO MINIMIZE BIAS

10.6.1 ENROLLMENT/ RANDOMIZATION/ MASKING PROCEDURES

Subjects will be screened and enrolled in two locations, neurology clinic and EMU. A total of 20 subject will be enrolled in each location and they will be randomized to drug vs placebo group equally (1:1) using computer generated random numbers. The assignment for each subject will be kept in a sealed envelope and will be provided to investigational drug pharmacy at the University of Iowa.

The participants as well as the investigators (except one) will be blinded to the drug the participant is receiving. Bottles of the study drug will be labelled with the name of study, drug A or drug B, and instruction of titration plan.

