4 STUDY DESIGN AND ENDPOINTS

4.1 DESCRIPTION OF THE STUDY DESIGN

Double blind placebo-controlled randomized prospective trial

Two enrolling locations: EMU and Neurology Clinic

1) To test effect of Fluoxetine on HCVR: Subjects will be screened in the EMU and neurology clinic. Subjects eligible are those with patients with epilepsy who have a reduced baseline HCVR slope (<2.0 L/min/mmHg). Subjects will be enrolled, and randomized to either fluoxetine or placebo (1:1) until 20 subjects complete the study. Investigational Drug Services (IDS), at the University of Iowa Hospitals and Clinics (UIHC), will be responsible for randomizing and dispensing the

Version 01.2 Protocol:201607761 Version 20.2 Version 01.2

drugs. Both fluoxetine and placebo will be encapsulated in identical casing to mask their identity. Both the subjects and the investigators will be blinded to the randomization process. A standard titration plan will consist of fluoxetine or placebo 10 mg per day for a week, then 20 mg per day for a week and then 40 mg per day for 2 weeks, upon discharge. Subjects will return after 4 weeks for follow up HCVR testing in the Clinical Research Unit at UIHC. For each subject, the magnitude of post-treatment HCVR in terms of HCVR slope, minute ventilation, VRTCO₂, time to VRTCO₂ and time to target ETCO₂ at the end of the study will be compared with their baseline HCVR. The medication adherence rate, safey concerns and change in mood scale will be assessed at follow up. Reported adverse effects will be collected for all subjects. Enrolment rate and study completion rates will also be assessed every 6 months.

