7.2 LABORATORY PROCEDURES/EVALUATIONS

7.2.1 CLINICAL LABORATORY EVALUATIONS

Urine pregnancy test (as applicable) will be done prior to HCVR.

HCVR testing in EMU:

Ultima PFX with gas chromatography machine will be used for HCVR testing. The machine will be operated by a well-trained respiratory therapist.

Subjects enrolled in EMU will have their baseline HCVR testing at the bedside either in a sitting up in their bed or in a chair. And those newly enrolled or follow up subjects in neurology clinic will have their

Version 01.2 Protocol:201607761 Version 20.2 Version 01.2

HCVR testing in CRU. Subject will wear a noise cancelling headphone and will be asked to look at a white/blank screen during the procedure.

The subjects will apply a nasal clip and then breathe through through a Y-valve that allows switching from room air to a 5-liter rebreathing bag filled with 50% oxygen, 6% carbon dioxide, and balance nitrogen. The test will begin with measurement of baseline respiratory parameters- respiratory rate, minute ventilation, tidal volume, ETCO₂, end-tidal oxygen breathing in room air for 2 minutes. They will then asked to hyperventilate to bring their ETCO₂ to 30 mm Hg.Then, they will be switched to a rebreathing bag. The subjects will be instructed to take 2 deep breaths promote rapid equilibration of PCO2 between the rebreathing bag and the alveolar, arterial and mixed venous compartments and then however they feel to make themselves comfortable.

The test will be terminated for: (1) ETCO₂ > 55 mm Hg; (2) ETO₂ < 160 mm Hg; (3) minute ventilation > 100 liters/minute; and/or (4) subject intolerance.

At the end of the test, the subjects will be asked to fill out questionnaire regarding their experience during the tests.

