10.4.2 ANALYSIS OF THE PRIMARY ENDPOINT(S)

Enrollment rate:

This will be assessed every 3 months until the end of the enrollment period. It will be reported as number of participants enrolled per 3 months. It will also be reported as percentage of all the patients screened.

Retention rate:

This will be assessed every 3 months. It will be reported as number of participants completed the study per protocol per 3 months. It will also be reported as percentage of all the patients screened.

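### Location (EMU or neurology clinic) has its own quota but no place in the planned reporting: feasibility counts and HCVR change should be given by, or adjusted for, location

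*Combined protocol and SAP*

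**What the plan says.** **Quotas and allocation.** Section 10.6.1: "A total of 20 subject will be enrolled in each location and they will be randomized to drug vs placebo group equally (1:1". The method is given as "using computer generated random numbers"; no stratification, blocking or separate list per location is stated. Section 4.1 describes two parts. In part 1 (effect on HCVR), "Subjects will be screened in the EMU and neurology clinic" and subjects are "randomized to either fluoxetine or placebo (1:1) until 20 subjects complete the study". Part 2 (peri-ictal respiration) takes clinic patients planned for video EEG, again 1:1 until 20 complete.

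**Test setting.** Section 7.2.1: "Subjects enrolled in EMU will have their baseline HCVR testing at the bedside". The same section places the testing of clinic subjects in the CRU. For follow-up, Section 4.1 part 1 says "Subjects will return after 4 weeks for follow up HCVR testing in the Clinical Research Unit at UIHC".

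**Reporting.** On enrolment, Section 10.4.2 says "It will be reported as number of participants enrolled per 3 months", and also gives it as a percentage of all patients screened. Completion is handled in the same way. Section 10.1 describes results by treatment group, Section 10.4.3 compares drug with placebo, and Section 10.4.8 plans no further subgroup analyses. Location is not named in any of them.

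**Interval.** The Protocol Summary and Sections 4.2.1 and 10.4.2 use 3 months for the primary measures. Section 4.1 says "Enrolment rate and study completion rates will also be assessed every 6 months".

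**The concern.** Feasibility is the primary objective (Section 3), and the pilot exists to supply estimates of centre and spread for later studies (Sections 10.1 and 10.4.1). Leaving location out can affect both.

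- **Recruitment.** Each location has its own target of 20, and the peri-ictal comparison depends on clinic patients. One combined count cannot show that one location is slow while the other makes up the difference. When the faster location fills, the combined count drops because a location has closed, not because recruitment capacity fell. Section 5.5 makes poor recruitment or completion a possible ground for stopping the study, so the figure may inform a decision.
- **HCVR change.** Only EMU subjects change test setting between baseline and follow-up. If setting affects the test, part of that effect enters the mean change in each arm and the SD of change, which are the numbers a later trial would use.

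**Working it through.** **1. The plan's own figure.** 2 locations × 20 = 40, which matches the forty subjects in the Protocol Summary. At the anticipated 2 per month (Section 5.3), 40/2 = 20 months, inside the 24-month study duration. Section 10.5 makes no formal sample size calculation, so there is no power figure to reproduce.

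**2. Recruitment.** The documents do not split the 2 per month by location, so the split is an assumption. The quotas are taken as enforced and accrual as steady.

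| EMU:clinic split | Rates per month | EMU full at | Clinic at month 24 | Clinic full at |
|---|---|---|---|---|
| 50:50 | 1.0 / 1.0 | 20/1.0 = 20 months | 20 | 20 months |
| 60:40 | 1.2 / 0.8 | 20/1.2 = 16.7 months | 0.8 × 24 = 19.2 | 20/0.8 = 25 months |
| 70:30 | 1.4 / 0.6 | 20/1.4 = 14.3 months | 0.6 × 24 = 14.4 | 20/0.6 = 33.3 months |

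In every row the combined count is 2 × 3 = 6 per quarter, exactly on plan, until the EMU fills. At 70:30 it then falls to 0.6 × 3 = 1.8 per quarter. The same holds with the locations exchanged.

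**3. Arm-level mean and SD of HCVR change.** Let d be the EMU-minus-clinic difference in mean change, in units of the within-location SD. The documents give no value for d. With half of each arm from each location:

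- the arm mean change shifts by d/2;
- pooled SD = within-location SD × √(1 + d²/4);
- a sample size based on the pooled SD is multiplied by 1 + d²/4.

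| d | Shift in arm mean (SD) | Pooled SD factor | Sample size factor |
|---|---|---|---|
| 0 | 0 | 1.000 | 1.00 |
| 0.5 | 0.25 | √1.0625 = 1.031 | 1.06 |
| 1.0 | 0.50 | √1.25 = 1.118 | 1.25 |

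For illustration, assume a later trial with a target of 0.5 SD, two-sided 0.05 and 80% power. It needs 63 per arm at d = 0, 67 at d = 0.5 and 79 at d = 1.0.

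**4. Drug-placebo difference.** The bias equals d × (EMU share in the drug arm − EMU share in the placebo arm). If arms are balanced within location, the bracket is zero and so is the bias. If randomisation is not stratified, with 20 per arm and 20 per location, the number of EMU subjects in the drug arm is hypergeometric. The shares then differ by 20 percentage points or more in about 34% of randomisations. At a 20-point gap the bias is 0.2 × 0.5 = 0.10 SD to 0.2 × 1.0 = 0.20 SD.

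**5. Cohort definitions.** Section 10.6.1 counts 20 enrolled per location. Section 4.1 counts 20 completing per part, and part 1 draws on both locations. Section 5.3 counts 20 completed in each group, which could mean arm or cohort. Section 4.1 part 2 mentions no follow-up HCVR, whereas Section 7.3.3 lists it without restriction. It is therefore unclear whether HCVR change covers one part or all 40 subjects.

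**The case against.** The case against is substantial.

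- **Nothing shows that setting matters.** Section 7.2.1 gives one test procedure for everyone, including headphones, a blank screen, the gas mixture and the stopping limits. This stands: d may be zero.
- **The SD inflation is small beside sampling error.** With 20 per arm (19 degrees of freedom, normal data), the 95% interval for an SD runs from about 0.76 to 1.46 times the estimate, and inflation errs on the cautious side for planning. This stands, and it argues against separate SDs from 10 subjects each, whose interval would be about 0.69 to 1.83. It does not argue against one SD pooled within location, nor does it address the shift in arm means.
- **The uneven accrual split is hypothetical, and a quota per location forces the team to count by location.** This stands in part. Staff would know of a shortfall, but the primary endpoint as defined would not show it.
- **Pooling is inferred from silence.** Correct. The models named in Section 10.4.3 could carry a location term; the plan simply does not name one.

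A reader might infer that the two locations are randomised from separate lists. The 1:1 wording suggests allocation within each location, but no stratified list is stated. A reader might also infer that the drug-placebo comparison is biased by setting. That needs both a setting effect and arms unbalanced by location, and the documents establish neither.

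**Conclusion.** The concern holds as a gap in specification whose size is unknown and probably modest. The text establishes the quotas by location, the setting change confined to EMU subjects, and the absence of any location split or term. It does not establish that the test setting shifts HCVR or that accrual will be uneven.

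The HCVR effect ranges from nothing at d = 0 to a 12% larger SD and a 25% larger planned sample at d = 1.0, assuming equal numbers from each location in each arm. The recruitment effect ranges from nothing at 50:50, through a shortfall of less than one subject at 60:40, to 14 of 20 clinic subjects at month 24 under 70:30. A reader might infer that a failing location could stay hidden throughout; in fact the combined count reveals the problem once the other quota fills, at about month 14 under 70:30.

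The 3- versus 6-month discrepancy for the primary measures is a genuine contradiction but a secondary point. The change is worth making because the pilot's product is its estimates and the cost is close to nil.

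**What to change.** 1. **Section 10.4.2:** report enrolment and completion for the EMU and the clinic separately, per month each location was open to enrolment, alongside the pooled figures. Change the interval in Section 4.1 to 3 months, to match Sections 4.2.1 and 10.4.2.
2. **Sections 10.4.3 and 10.4.11:** include enrolling location as a fixed effect in the drug-placebo comparison of HCVR changes. For planning, report the location-adjusted residual SD, pooled within location.
3. **Sections 10.6.1, 4.1 and 5.3:** state whether randomisation is stratified by location. Settle whether the 20s count enrolled or completed subjects, whether they apply per location, per part or per arm, and which subjects contribute to HCVR change.

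The cost is one extra table and one degree of freedom: with 40 subjects, 40 − 3 = 37 residual degrees of freedom instead of 40 − 2 = 38. No new data, visits or patients are needed.

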7.3.3 FOLLOW-UP

Follow up phone call at end of week 1 and 3

Record for adverse events as reported by the participants.

If suspicious for mania, will perform full Altman self-report maniac scale

Record compliance to assigned treatment as reported by the participants.

Record current medication

Follow up visit 4 weeks (+/-1 week) after randomization

Record for adverse events as reported by the participants.

Record compliance to assigned treatment as reported by the participants and by counting pill from the pill container brought by the participants.

Record PHQ-9 score

Repeat HCVR testing

Record current medication

Video EEG study with comprehensive respiratory monitoring in EMU for paticipants enrolled at neurology clinic

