8.2.2 RELATIONSHIP TO STUDY AGENT

For all collected AEs, the clinician who examines and evaluates the participant will determine the AE's causality based on temporal relationship and his/her clinical judgment. The degree of certainty about causality will be graded using the categories below.

- **Definitely Related** There is clear evidence to suggest a causal relationship, and other possible contributing factors can be ruled out. The clinical event, including an abnormal laboratory test result, occurs in a plausible time relationship to drug administration and cannot be explained by concurrent disease or other drugs or chemicals. The response to withdrawal of the drug (dechallenge) should be clinically plausible. The event must be pharmacologically or phenomenologically definitive, with use of a satisfactory rechallenge procedure if necessary.
- **Probably Related** There is evidence to suggest a causal relationship, and the influence of other factors is unlikely. The clinical event, including an abnormal laboratory test result, occurs within a reasonable time after administration of the drug, is unlikely to be attributed to concurrent disease or other drugs or chemicals, and follows a clinically reasonable response on withdrawal (dechallenge). Rechallenge information is not required to fulfill this definition.
- **Possibly Related** There is some evidence to suggest a causal relationship (e.g., the event occurred within a reasonable time after administration of the trial medication). However, other factors may have contributed to the event (e.g., the participant's clinical condition, other concomitant events). Although an AE may rate only as "possibly related" soon after discovery, it can be flagged as requiring more information and later be upgraded to "probably related" or "definitely related," as appropriate.
- Unlikely to be related A clinical event, including an abnormal laboratory test result, whose temporal relationship to drug administration makes a causal relationship improbable (e.g., theevent did not occur within a reasonable time after administration of the trial medication) and inwhich other drugs or chemicals or underlying disease provides plausible explanations (e.g., the participant's clinical condition, other concomitant treatments).

Version 01.2 Protocol:201607761 06/28/2017

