8.5 STUDY HALTING RULES

Administration of study agent will be halted when three grade 3 (severe) AEs determined to be "probably related" are reported to the IME. The IME will notify the study sponsor and investigators immediately when the third grade 3 event is reported and enrollment screens will stop accepting new study participants. The study sponsor will provide the IME with AE listing reports within 24 hours. The IME will provide recommendations for proceeding with the study to the study sponsor. The study sponsor may inform the FDA of the temporary halt and the disposition of the study.

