8.6 SAFETY OVERSIGHT

Safety oversight will be under the direction of an independent medical examiner (IME). The IME will assess safety and efficacy data on each arm of the study. The IME will provide its input to IRB, sponsor and principal investigator

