10.6.3 BREAKING THE STUDY BLIND/PARTICIPANT CODE

The blinding would be broken in the circumstance of severe adverse events. The treating physicians will be unblinded. Both intentional and unintentional unblinding will be reported to IME.

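### Bottles carry one of two shared letters, so under a single key one code break reveals the arm of any other participant whose letter is known; a unique number per participant would be a cheap, minor improvement

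*Combined protocol and SAP*

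**What the plan says.** All references are to the combined protocol and SAP.

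- **Labelling (10.6.1).** "Bottles of the study drug will be labelled with the name of study, drug A or drug B, and instruction of titration plan". Capsules are identical in appearance (4.1, 6.1.2, 6.1.4), but that does not hide the letter on the bottle.
- **Allocation (10.6.1).** Randomisation is 1:1. "A total of 20 subject will be enrolled in each location", and there are two locations. "The assignment for each subject will be kept in a sealed envelope", and the envelopes go to the investigational pharmacy.
- **Code break (10.6.3).** "The blinding would be broken in the circumstance of severe adverse events. The treating physicians will be unblinded". Any unblinding is reported to the independent medical examiner (IME). No step is given to protect the blind of other participants.
- **Contact with the container (7.3.3).** At the week 4 visit AEs are recorded, and staff are to "Record compliance to assigned treatment as reported by the participants and by counting pill from the pill container brought by the participants".
- **AE judgments (8.2.2).** For every AE, "the clinician who examines and evaluates the participant will determine the AE's causality based on temporal relationship and his/her clinical judgment".
- **Blinding check (10.6.2).** Marked not applicable.

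Nothing in the document says whether A and B keep the same meaning for every participant, and nothing describes kit numbers or re-keying.

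**The concern.** With two arms and two letters, decoding one letter decodes the other. There are two ways this could happen.

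1. **After a code break.** A person who learns the broken participant's arm, and knows that participant's letter, then knows the arm of anyone else whose letter they have seen.
2. **Without a break.** If the container brought to the week 4 visit is the labelled bottle, staff who see the letters could tally side effects by letter and form a better-than-chance guess.

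The data at stake belong to participants who are still on treatment or not yet randomised when the letters are decoded. They are the causality and severity judgments for those participants' AEs, the between-arm AE comparison in 10.4.4, and possibly the duration of abnormal peri-ictal breathing (10.4.3) if the scorer knows the letters. The document does not say who scores it. Section 10.1 presents the study as a source of estimates for later trials, so a distorted AE or breathing comparison would carry forward. Because 10.6.2 plans no assessment of blinding, a wider loss of the blind would not show up.

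**Working it through.** The plan gives no figure on this point, so there is none to reproduce. As a consistency check, 2 locations × 20 = 40, which agrees with the forty randomised in the Protocol Summary.

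**Reach of one break, by counting.** If N participants share a key, one break fixes both letters and can reveal at most N − 1 others.

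- One key for the trial: 40 − 1 = 39.
- A separate key per location: 20 − 1 = 19.
- A unique code per participant: 0.

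These are ceilings. They apply only to someone who knows all the letters, and they include participants who have finished. They also rest on 40 being randomised. Sections 4.1 and 5.3 continue until a number *complete*, so the total could be somewhat larger.

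**How often a break might occur (illustration only).** The document gives no severe-AE risk, so p is assumed at 1% to 10% per participant.

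- Chance of at least one break = 1 − (1 − p)^N.
- Expected number randomised after the first break = Σ over k = 1..N of p(1 − p)^(k−1) × max(N − k − L, 0), counting zero when no break occurs.
- L is the number randomised between a participant's start and the event. With 6 weeks of treatment (6.1.9) and 2 per month (5.3), 6/4.345 × 2 = 2.8, taken as 3. For one location, assuming an even split of 1 per month, 6/4.345 × 1 = 1.4, taken as 1.

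| Assumed p | At least one break, N = 40 | Randomised afterwards, of 40 (L = 3) | At least one break, N = 20 | Randomised afterwards, of 20 (L = 1) |
|---|---|---|---|---|
| 1% | 33.1% | 5.9 | 18.2% | 1.6 |
| 2% | 55.4% | 10.7 | 33.2% | 3.1 |
| 5% | 87.1% | 20.0 | 64.2% | 6.6 |
| 10% | 98.5% | 27.2 | 87.8% | 10.4 |

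The range is too wide to support a probability statement. The result also depends heavily on whether the key is trial-wide or per location.

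**Guessing without a break.** Assume a side effect with risk p0 of 10% or 20% on placebo, and p1 higher by 10 or 20 percentage points on drug.

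- Guess from one participant's own experience: 0.5 + (p1 − p0)/2 = 0.55 or 0.60.
- Guess from counts pooled by letter: P(X1 > X0) + 0.5 × P(X1 = X0), where X1 and X0 are binomial with n participants per letter.

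| n per letter | 10% v 20% | 10% v 30% | 20% v 30% | 20% v 40% |
|---|---|---|---|---|
| 3 | 0.616 | 0.713 | 0.604 | 0.695 |
| 5 | 0.659 | 0.779 | 0.637 | 0.751 |
| 10 | 0.729 | 0.870 | 0.694 | 0.835 |

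Pooling is weak early on. It becomes informative only around 10 per letter, which is half the trial under one key, and only if someone keeps a tally by letter.

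**Does the label affect the halting rule?** Section 8.5 reads "Administration of study agent will be halted when three grade 3 (severe) AEs determined to be" probably related. Only severe events count. Section 10.6.3 breaks the blind for severe events. So each event that can count already leads to unblinding of that participant's own treating physicians, whatever is printed on the bottle.

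**The case against.** Three stronger readings are tempting, and the documents support none of them.

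- **A reader might infer that the labels compromise the halting rule.** They add little there, for the reason shown in the working. A contribution remains only if causality is judged before the participant's own break, by a clinician who learned an earlier result and knows the letters. The document does not describe that sequence. After the third event the IME receives AE listings and advises on how to proceed, and 8.5 describes the halt as temporary.
- **A reader might infer that one severe AE unblinds the trial.** A constant key is not stated. Section 10.6.3 names treating physicians as those unblinded and reports the event to the IME. No section says that these physicians see other participants' bottles, judge their AEs or score outcomes.
- **A reader might infer that allocation concealment fails.** The sealed envelopes still conceal assignments not yet dispensed. What they do not protect is a participant already holding a lettered bottle.

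It is also fair to say that little in this pilot turns on the blind. The primary endpoints are recruitment and retention, 10.2 states no hypothesis, and 10.4.1 rules out inferential tests. Section 7.3.3 refers to a pill container, which may not be the labelled bottle. Investigational Drug Services already randomises, labels and dispenses (4.1, 6.2), and 8.6 already provides that "The IME will assess safety and efficacy data on each arm of the study".

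All of this limits the size of the point. It does not remove it: the plan states a two-code label, plans code breaks, and gives no other safeguard for participants already holding bottles.

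**Conclusion.** The point holds as a minor masking weakness. If one key is used throughout, a code break decodes the arm of any other participant whose letter is known to someone who learns the result. Pooling side effects by letter is a second, weaker route.

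The added exposure is confined to participants still on treatment or not yet randomised at the time. It concerns their AE causality and severity judgments, the AE comparison in 10.4.4, and possibly peri-ictal breathing scores. Recruitment, retention and data collected before a break are little affected.

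The ceiling is 39 others with one key or 19 with a key per location, and the true spread is unknown. The conclusion rests on a constant key and on letters being visible to someone who also learns a result. The break probabilities and side-effect risks are assumptions and carry no weight in it.

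**What to change.** In 10.6.1, replace the two letters with a unique participant or randomisation number on each bottle. State that Investigational Drug Services holds the key and releases it one participant at a time for a code break, and by arm only to the IME for the review in 8.6. A break then directly discloses no one but the participant concerned, and side effects cannot be pooled by label. The change does not alter who is unblinded for that participant.

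The cost is slightly more labelling work for the pharmacy and a short amendment. Capsules, randomisation list and envelopes stay as they are.

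Separately, reconcile 4.1, which describes the investigators as blinded to the randomisation process, with 10.6.1, which excepts one investigator without defining that person's role. State that this person takes no part in enrolment, outcome assessment or AE causality.
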